10.1.3.3. Area of Autograft in DPT Wounds

Very few cases of missing data are expected to be observed in the secondary endpoint of percentage of wound area autografted in DPT wounds. Any missing data for percent area autografted will be imputed using the multiple imputation method. The procedure can be described as follows:

- 1. Imputation: The imputation model will be built on a subject level by multiple linear regression of known percent area autografted on center, total area of TWs, %TBSA, number of TWs (1,2,3-4,≥5), age and sex, and will be carried out separately within each treatment group. Once the model is estimated, the imputed values will be obtained from the value predicted by the model plus a residual term that will be drawn at random from the estimated residuals. The random seed will be 141421. Twenty five (m=25) imputed datasets will be created.
- Analysis: Each of the m complete datasets will be analyzed using a linear regression model. The explanatory variables in the model will include treatment, center, age, %TBSA, proportion of the FT area of a patient and number of TWs (1,2,3-4,≥5). An

estimated treatment difference, δ (NexoBrid versus SoC), from the analysis model and a two-sided p-value, p, from the permutation test (as described in Section 11.1.2) will be obtained for each imputed dataset.

3. Pooling: The m analysis results will be integrated into a final result – an overall estimate of δ , its standard error, and the final p-value, as described in Section 10.1.3.2 (items 4 and 5).

10.1.3.4. Incidence of Autograft in DPT Wounds

Little or no missing data are expected for the secondary endpoint incidence of Autograft performed in deep partial thickness wounds. The main analysis (on a target wound level) will include only DPT target wounds from all randomized patients, with those having a missing value assumed to have "failed", i.e. to have received autograft. Two sensitivity analyses will be performed. First, in each treatment group, only DPT target wounds with documented Autograft will be counted and this number divided by the total number of DPT target wounds from randomized subjects with non-missing endpoint (i.e. wounds with missing values will be excluded, a complete case analysis). A second analysis will include DPT target wounds from all randomized patients and count all wounds with missing data (for this endpoint) as "success" (i.e. no autograft performed).

Note: The main analysis specified in the protocol was the complete case analysis. However, for the same reasons as detailed for the secondary endpoint incidence of surgical excision (see 10.1.3.1), the main analysis will be based on DPT target wounds from all randomized subjects.

10.1.4. Safety Endpoints

10.1.4.1. Time to Reach Complete Wound Closure

The analyses of the safety endpoint time to complete wound closure on a target wound level will compute missing values as censored at the date of the last non-missing wound closure assessment. If no wound closure assessment after baseline is available, the target wound will be censored with time 0.

For additional analyses on a subject level, if a subject has a wound which did not reach complete closure, the time will be censored at last date of wound closure assessment. If a

subject has a wound with no wound assessment available after baseline, the subject will be censored with time 0.

Note: the additional analysis on a subject level had been added per FDA recommendation.

has the last non-missing MVSS value before the 24 months' measurement for the individual as explanatory variable. To this prediction, the realization of a normally distributed random variable with zero mean and standard deviation equal to the residual standard deviation from the linear model is added. The random seed for this imputation is 45448.

Using this imputation method deviates from the handling of missing data specified in the protocol. There, simple LOCF was intended. However, LOCF is not considered a suitable imputation method for the MVSS values as early MVSS values are not considered predictive for late MVSS measurements in the same individual. Furthermore, LOCF is heavily criticized in the statistics community since it may lead to biased results even when the missing occurs completely at random (see [17], [18]).

Additionally, best case – worst case imputations will be used as a supporting sensitivity analysis. One using the worst case MVSS value of 9 (observed maximum MVSS value in the SoC group in the previous study MW2004-11-02) for all missing MVSS data and one using the best case value of 0 (observed minimum MVSS value in the SoC group in the previous study MW2004-11-02).

10.1.4.3. Cosmesis and Function at 24 Months from Wound Closure

See 10.1.4.2.

10.1.4.4. General Parameters of Safety

Lower Extremity Functional Scale

The calculation of the total score will be made if less than or equal to 10% of the items were left blank. If more than 10% of items are missing the score cannot be calculated. In the event of missing items, the total score will be adjusted by dividing the total by the proportion of completed items.

Disabilities of the Arm, Shoulder and Hand (Quick-DASH)

The calculation of the total score will be made if less than or equal to 10% of the items were left blank. If more than 10% of items are missing the score cannot be calculated.

Range of Motion (ROM) (at 12 and 24 months)

In case of missing data of ROM, LOCF will be used for imputation. If a subject has no ROM measurement at all, it will be excluded from the general linear model analysis of the ROM.

EQ-5D (Quality of Life)

Missing EQ-5D values will not be imputed, but form a separate category in the analysis of this endpoint.

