For the definition of pCS high and pCS low, see Section 13.2.2.

Lower Extremity Function Scale (LEFS)

The LEFS will be assessed at the following time points: at 6, 12 weeks and months 6, 12, 18 and 24 after wound closure. It consists of 20 items which can each be answered on a scale of 0 to 4. In the database the answers will be coded as 1 to 5. Therefore, the total LEFS for a patient will be computed as

$$LEFS = \sum_{i=1}^{20} a_i - 20,$$

where a_i is the answer to item i (coded 1 to 5). As indicated in Section 10.1.4.4, the calculation of the total score will be made if less than or equal to 10% of the items were left blank. If more than 10% of items are missing the score cannot be calculated. In the event of missing

items, the total score will be adjusted by dividing the total by the proportion of completed items, as follows:

$$LEFS = \frac{\sum_{i=1}^{k} a_i}{k/20} - 20$$

where k is the number of completed items and a_i are the non-missing values.

Disabilities of the Arm, Shoulder and Hand (QuickDASH)

The QuickDASH will be assessed at the following time points: at 6, 12 weeks and months 6, 12, 18 and 24 after wound closure. It consists of 11 items which are scored 1-5. As indicated in Section 10.1.4.4, the calculation of the total score will be made if less than or equal to 10% of the items were left blank. If more than 10% of items are missing the score cannot be calculated. Hence, at least 10 of the 11 items must be completed for a score to be calculated. The assigned values for all completed responses are simply summed and averaged, producing a score out of five. This value is then transformed to a score out of 100 by subtracting one and multiplying by 25. Hence, the QuickDASH score for a single patient is calculated by:

$$QuickDASH = \left(\frac{sum\ of\ n\ responses}{n} - 1\right) * 25.$$

Range of Motion (ROM)

For each visit (12 months FU and 24 months FU), a binary (yes/no) variable will be calculated, indicating whether the range of motion assessment for that patient was abnormal or not. The range of motion assessment will be considered abnormal, if the measurement of at least one joint under consideration does not lie within the normal ranges of motion given in appendix 13 of the study protocol at the respective time point. For handling of missing data see Section 10.1.4.4.

EQ-5D (Quality of Life)

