10.5.1. Handling of Missing Values

Data missing due to COVID-19 will be handled in the same way as missing data for any other reason, i.e. the procedures for handling of missing data described in the SAP in Section 10.1 will also be applied to missing values due to COVID-19.

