10.5.2. Handling of Remotely Captured Data

Due to COVID-19 restrictions, the sponsor has submitted a protocol memo (see SAP Section 13.4), dated 09 Apr 2020, to sites allowing them to perform long-term follow-up visits

remotely. All visits could have been performed remotely, but at the time of COVID-19 outbreak almost all patients had already been post 12 weeks FU visit, so it is expected a large portion of remote assessments starting from the 6 months FU visit and onwards.

Apart from MVSS and POSAS assessments, all endpoints, allowed to be evaluated remotely during long-term follow-up visits, are self-reported. Therefore, no influence of remote study visits is expected. For MVSS and POSAS assessments, the possible influence of remotely captured data will be addressed as described in the following sub-sections.

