POS	SAS Observer Scale	х		X	Video method preferred, if available
	MVSS	Х		X	Video method, if available
	ROM	N/A	N/A	N/A	Can be completed during an on-site visit only.
	POSAS Patient Scale	X Photocopy sent back to site	X Subject interview	X Subject interview	It is preferred to have questionnaires sent to subject via mail/email, completed, and returned to site, if possible.
Patient	QOL (EQ5D,BOQ)	X Photocopy sent back to site	X Subject interview	X Subject interview	It is preferred to have questionnaires sent to subject via mail/email, completed, and returned to site, if possible.
questionnaires	LEFS/ QuickDASH	X Photocopy sent back to site	X Subject interview	X Subject interview	It is preferred to have questionnaires sent to subject via mail/email, completed, and returned to site, if possible.
	Subject Diary	X Photocopy sent back to site	X Subject interview	X Subject interview	It is preferred to have questionnaires sent to subject via mail/email, completed, and returned to site, if possible.
Immunogenicity		N/A	N/A	N/A	Can be taken during an on-site visit only. May be performed in delay

Statistical Analysis Plan V02 of 31 May 2021

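### Missing 12- and 24-month range of motion is filled by LOCF, a method the SAP criticises in general terms when dropping it for MVSS, and no sensitivity analysis is planned

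*SAP*

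**What the plan says.** - **The ROM rule.** SAP 10.1.4.4, for 12 and 24 months: "In case of missing data of ROM, LOCF will be used for imputation". A subject with no ROM value at all is left out.
- **The endpoint.** SAP 10.3.4.4 reduces ROM to one yes/no result per patient at each of these two visits. The rule, cut short here before it cites its reference values, reads: "The range of motion assessment will be considered abnormal, if the measurement of at least one joint under consideration does not lie within the normal". SAP 11.1.5.17 and 11.2.4.8 compare the arms by logistic regression in subjects with joint injury.
- **LOCF elsewhere.** SAP 10.1.4.2 abandons LOCF for MVSS for two reasons. One is specific: "LOCF is not considered a suitable imputation method for the MVSS values as early MVSS values are not considered predictive for late MVSS measurements". The other is general: "LOCF is heavily criticized in the statistics community since it may lead to biased results even when the missing occurs completely at random".
- **Remote visits.** In the table of remote methods in SAP 13.4, ROM is not available by photo, phone or video: "Can be completed during an on-site visit only". SAP 10.5.2 says "it is expected a large portion of remote assessments starting from the 6 months FU visit and onwards".
- **COVID-19 gaps.** SAP 10.5.1: "Data missing due to COVID-19 will be handled in the same way as missing data for any other reason".

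**The concern.** The specific reason for dropping LOCF concerns MVSS only, but the general one concerns the method and applies equally to a ROM value carried forward. ROM is also exposed to missing data, because every visit held remotely yields no ROM value.

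SAP 10.5.2 discusses only endpoints that may be assessed remotely: the self-reported ones, MVSS and POSAS. ROM is neither remote-capable nor self-reported, so it is not considered there. MVSS receives regression imputation, best- and worst-case analyses and a correction for remote data. ROM receives LOCF with no alternative analysis and no planned count of carried values.

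At stake is whether the 12- and 24-month ROM comparisons describe those time points. A carried value mixes an earlier stage of recovery into the later comparison, and the logistic model counts it as a real observation.

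**Working it through.** **1. How a missing value reaches the test.** A remote visit gives no ROM (13.4). The gap is handled under Section 10.1 (10.5.1), which for ROM means LOCF (10.1.4.4). The filled value enters the logistic model (11.1.5.17, 11.2.4.8). The study schedule (7.1, Table 1) places ROM at weeks 6 and 12 and months 6, 12, 18 and 24. A filled 12-month value can therefore date from week 6, week 12 or month 6, and a filled 24-month value from any visit up to month 18.

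**2. Figures in the plan.** No sample size, missing rate or joint-injury count is given for ROM, so there is no ROM figure to reproduce. The nearest planning figures are the MVSS retention rates in SAP 13.3: q = 0.7 at 12 months and 0.5 at 24 months. They reproduce the stated MVSS sample sizes:

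n = 2(1.96 + 1.28)² × 2.33² / [q(−0.26 − 1.9)²]

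- q = 0.7: 34.90, so 35 per group (stated: 35)
- q = 0.5: 48.86, so 49 per group (stated: 49)

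**3. Possible counts.** Assume these losses applied to ROM and every affected subject had an earlier value. Carried-forward results = 145 × joint-injury share × loss. The shares are assumed.

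| Joint-injury share | 12 months (30%) | 24 months (50%) |
|---|---|---|
| 100% | 43.5 of 145 | 72.5 of 145 |
| 50% | 21.8 of 72 | 36.2 of 72 |
| 25% | 10.9 of 36 | 18.1 of 36 |

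**4. Effect on an abnormal rate.** Reported rate = (1 − m) × true late rate + m × earlier rate, where m is the share carried forward. Assume 25% abnormal at 12 months and m = 0.3.

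- Carried values with 50% abnormal: 0.7 × 25 + 0.3 × 50 = 32.5%
- Carried values from a nearer visit with 30% abnormal: 0.7 × 25 + 0.3 × 30 = 26.5%

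The distortion depends strongly on which visit supplies the value.

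**5. Effect on the arm difference.** With equal m in both arms, reported difference = (1 − m) × late difference + m × earlier difference. All rates below are assumed.

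*Masking.* Late rates are 15% (SoC) and 35% (NexoBrid), the earlier rate is 35% in both arms, and all 145 are analysed (72.5 per arm). At m = 0.3 the SoC rate becomes 0.7 × 15 + 0.3 × 35 = 21%, and the 20-point difference falls to 14. At m = 0.5 it becomes 25%, and the difference falls to 10. Power = Φ[(difference − 1.96 × SE₀)/SE₁], where SE₀ is pooled and SE₁ unpooled:

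| | No missing data | m = 0.3 | m = 0.5 |
|---|---|---|---|
| LOCF | 80% | 47% | 26% |
| Complete cases (MCAR) | 80% | 65% | 50% |

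*The opposite case.* With an earlier difference of 20 points and no late difference, LOCF reports 0.3 × 20 = 6 or 0.5 × 20 = 10 points where there are none.

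The bias can therefore go either way, and the documents do not say which case is nearer the truth.

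**The case against.** The strongest reply is that the SAP judges LOCF unsuitable for MVSS, says only that LOCF may lead to bias, and never says that early ROM fails to predict late ROM. That is fair. The inconsistency rests on the general criticism alone, and it is an unexplained difference in treatment rather than a flat contradiction.

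A reader might go further and infer that most 12- and 24-month ROM results will really be week-6 or week-12 values, so that the comparison reflects early healing. The documents do not support this:

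- The statement in SAP 10.5.2 can be read as saying at which visits remote assessments would fall, not that most visits would be remote.
- The memo in SAP 13.4 allows a remote visit only where an on-site one is not feasible and cannot be rescheduled, and on-site visits resume once restrictions end.
- Enrolment was running before May 2017 (13.1) and ended by March 2020 (13.3), so some late visits could precede the pandemic.
- LOCF takes the latest value available, which may be month 6 for the 12-month analysis and month 12 or 18 for the 24-month analysis.
- The 30% and 50% losses are MVSS planning assumptions, which SAP 13.3 itself calls conservative.

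The consequence is also limited. ROM is listed among the additional safety measures (protocol synopsis, item 4b), is analysed only in subjects with joint injury, and is outside the hierarchy in SAP 11.1.9. SAP 11.2.8 calls all second-stage testing exploratory. LEFS and QuickDASH also inform function, can be collected remotely and have no LOCF rule.

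None of this supplies a reason to keep LOCF as the only ROM analysis.

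**Conclusion.** The point holds as a matter of consistency and inexpensive bias reduction. Under the SAP as written, some 12- and 24-month ROM results will be earlier measurements analysed as observed, with standard errors that ignore the imputation and no analysis to show whether this matters.

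Neither the number of such results nor the size and direction of the bias can be derived from the documents. The counts, rates and power values above are illustrations under stated assumptions, not estimates. The primary and secondary efficacy conclusions do not depend on ROM. What is affected is the reading of one long-term functional safety measure.

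Two gaps belong with this point. SAP 10.1.4.4 refers to a general linear model for ROM, whereas 11.1.5.17 and 11.2.4.8 specify logistic regression. The SAP also does not say whether LOCF applies joint by joint or to the patient-level result.

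**What to change.** 1. Derive the yes/no ROM result at every scheduled follow-up visit, not only at 12 and 24 months.
2. Make the main analysis either a mixed logistic model on observed on-site ROM, with treatment contrasts at 12 and 24 months, or multiple imputation by logistic regression within arm, using earlier ROM and the stratification factors and pooled by Rubin's rules. At the first stage, use data only to month 12, since SAP Section 11 keeps 24-month data out of that analysis.
3. Do not copy the MVSS method. It is a single random draw from a linear model with normal residuals, which does not suit a binary endpoint and also treats imputed values as observed.
4. Keep observed-case and LOCF analyses as sensitivity only. State whether LOCF works per joint or per patient.
5. Report observed, missing and carried-forward counts by arm and visit.
6. Replace the reference to a general linear model in 10.1.4.4 with logistic regression.

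The cost is SAP wording, a little more programming and somewhat wider intervals. No new data are needed.

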10.1.5. Exploratory Endpoints

10.1.5.1. POSAS

The Patient Observer Scar Assessment Scale (POSAS) consists of two parts: a patient scale and an observer scale. Both scales contain six items that are scored numerically with 1-10. If for a wound an item of the observer scale is missing the respective value will be imputed by the mean value of the other items from the observer scale of that wound. Analogously, if for a wound an item of the patient scale is missing the respective value will be imputed by the mean value of the other items from the patient scale of that wound.

If more than one value is missing within a scale for one wound, the respective scale and the overall POSAS value for that wound (see Section 10.3.5.7) will not be calculated and regarded as missing value.

10.2. Handling of Withdrawals and Dropouts

Withdrawn subjects will be evaluated in the FAS and safety set. Missing values are imputed as mentioned in Section 10.1.

Subjects with premature study discontinuation before end of the efficacy assessment period (i.e. before the 12 weeks follow-up post wound closure confirmation) lead to problems for analyses which include data from re-admissions. If a subject discontinued study participation during the efficacy assessment period, it is not known whether the subject had a(nother) readmission and data are missing. Consequently, the corresponding variables will be set to missing for all those subjects except for "Lost-to-follow-ups" who completed the eschar

removal treatment. The exception is done under assumption that subjects who are lost to follow up would have come back for re-admission if this had been necessary (Without this exception a lot of information would have been lost in MW2010 since the percentage of subjects with readmission is higher for "Lost-to-follow-ups" then for the rest of the population).

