6.1. General Definitions of Medical Terms

Full analysis set (FAS): The full analysis set includes all patients who are randomized into the trial. The analysis is focused on the planned treatment.

Complete eschar removal: is achieved at the end of the eschar removal treatment phase. The Eschar Removal assessment should be more or equal to 95% and will be clearly marked as the end of the eschar removal process and the initiation of specific treatment aimed to close the viable debrided bed by grafting or epithelialization [14].

Complete wound closure: defined as % of wound area epithelialized and/or closed by graft is >95% without drainage or dressing requirements confirmed at two consecutive study visits, 2 weeks apart.

Efficacy assessment period: defined as the time period up to the 12 weeks follow-up post wound closure confirmation.

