10.3.4.4. General Parameters of Safety

Volume of Blood Transfusions Given

The volume of blood transfusions given during hospitalization (including readmissions) will be according to the volume (in milliliters) of whole blood and packed red blood cells transfused, presented separately, as collected on eCRF. In addition, Transfusion RBC Volume (in milliliters) will be calculated using the following formula [15], [48]:

Transfusion RBC Volume (mL)

- = $[Total\ Volume\ (mL)\ of\ Whole\ Blood\ Transfused \times 0.3]$
- + [Total Volume (mL) of Packed Red Blood Cells Transfused \times 0.8]

For subjects who discontinued study participation during the efficacy assessment period, it is not known whether a(nother) transfusion occurred and relevant data are missing. Consequently, the variable is set to missing for all those subjects except for "Lost-to-follow-ups" who completed the eschar removal treatment. The exception is done under the assumption that subjects who are lost to follow up would have come back for readmission if this had been necessary (see also safety endpoint "rates of hospital readmission").

Analgesia and Anesthesia

Relevant analgesia and anesthesia medications will be presented in the concomitant medications tables.

Antibiotic Use

The number of days of exposure to systemic antibiotic drugs will be calculated for each patient. This will be done overall and also for antibiotic use due to AE involvement (as indicated in the eCRF) and for prophylactic antibiotic use (as indicated in the eCRF) separately.

Only records with ATC level 2 equal to "ANTIBACTERIALS FOR SYSTEMIC USE" are used. In case of a missing start date for a medication marked as pre-existing, the start date is imputed by the date of informed consent. In case of a missing stop date for a medication ongoing at study termination, the stop date is imputed by the study termination date. No other imputation is planned, i.e. if the start or stop date for antibiotics is missing, the days of antibiotic use will be counted as missing for the respective subject.

The calculation of the number of days only considers days between randomization and wound closure confirmation. Each day is only counted once; the actual frequency is not considered. Values for subjects with premature study discontinuation prior to the end of the efficacy assessment period are set to missing.

Rates of Hospital Readmission

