For each patient a binary (yes/no) variable will be computed indicating whether this patient had a hospital readmission or not. Additionally, for each hospital readmission, a binary (yes/no) variable will be collected indicating whether this readmission was planned or not. A readmission will be considered as being planned when the reason for readmission was indicated as "planned wound management" or "scar modulation" in the eCRF. Readmissions for which the reason was given as "AE" in the eCRF are considered as being unplanned. Hospital readmission for which the reason is given as "other" will be reviewed by the sponsor in order to decide whether they are to be classified as planned or unplanned.

Furthermore, a variable giving the number of planned hospital readmissions and a variable giving the number of unplanned readmissions will be computed for each patient.

Relative and absolute frequencies of hospital readmission (overall, planned, and unplanned) will be calculated per treatment arm.

For subjects who discontinued study participation during the efficacy assessment period, it is not known whether a(nother) readmission occurred and relevant data are missing.

Consequently, the variable is set to missing for all those subjects except for "Lost-to-follow-ups" who completed the eschar removal treatment. The exception is done under the assumption that subjects who are lost to follow up would have come back for readmission if this had been necessary (Without this exception a lot of information would have been lost in MW2010 since the percentage of subjects with re-admission is higher for "Lost-to-follow-ups" then for the rest of the population).

Change in PTT/INR

Change in PTT/INR will be computed as PTT/INR on $4h \pm 15$ min post first application (NexoBrid arm) respectively to 4h post first SoC treatment (SoC arm) minus PTT/INR pre the respective procedure for each patient.

For the classification of normal and abnormal PTT/INR values (low or high), the reference limits of the local labs will be used. If INR reference ranges will not be available for specific sites, common normal range of 0.8-1.2 will be used for these sites [19].

In addition, for each subject, for each parameter (INR/PTT) a variable will be computed, indicating whether the 4 hour post first treatment measurement was post treatment potentially clinically significant high (pCS high) or post treatment potentially clinically significant low (pCS low).

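### The SAP blanks readmissions and transfusion volumes already observed in some early discontinuers and assumes no later event in others, so these safety summaries can be biased in either direction

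*SAP*

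**What the plan says.** The rule concerns patients who discontinue during the efficacy assessment period, which SAP Section 6.1 has "defined as the time period up to the 12 weeks follow-up post wound closure confirmation".

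- **General rule (Section 10.2).** The reason given is that "it is not known whether the subject had a(nother) readmission and data are missing". Hence "the corresponding variables will be set to missing for all those subjects except for" patients lost to follow-up who had completed eschar removal. Those patients keep what was recorded, on the assumption that "subjects who are lost to follow up would have come back for re-admission if this had been necessary". The SAP adds that without the exception much information would have been lost in MW2010, since "the percentage of subjects with readmission is higher for" lost-to-follow-ups than for the remaining patients.
- **Readmission (Section 10.3.4.4).** The variable is yes/no per patient, with counts of planned and unplanned readmissions alongside. The reason is repeated: "it is not known whether a(nother) readmission occurred and relevant data are missing". It is then blanked in the same way, with the same lost-to-follow-up group excepted.
- **Transfusion volume (Section 10.3.4.4).** The reason is that "it is not known whether a(nother) transfusion occurred and relevant data are missing", with the same consequence and the same exception.
- **Analysis.** Section 11.1.5.13 compares readmission by chi-square or Fisher's exact test. Section 11.1.5.8 compares mean transfusion volume by one-way ANOVA, and presents it overall and for four periods: before treatment, during eschar removal, within one week afterwards, and later. Neither section plans a censored or sensitivity analysis.

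**The concern.** The reason given for blanking the variable is that a further event may have gone unseen. That does not justify removing what was seen. One recorded readmission fixes the yes/no variable at yes, whatever happens afterwards. A child who completes eschar removal and withdraws weeks later has a fully known transfusion volume for that period, yet the missing-value rule makes no distinction by period. The SAP uses the loss of information to justify keeping the data of lost patients, but does not apply that reasoning to other discontinuers.

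The excepted patients raise a different problem. They stay in the denominator and are treated as having no event after they disappear.

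At stake are the readmission percentages, the transfusion means and their between-arm tests. In an open-label trial, discontinuation or its link with readmission could differ by arm. The comparison would then be distorted as well as the level.

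**Working it through.** **No stated figure to reproduce.** The documents give no readmission rate, no transfusion volume for this trial, no dropout rate for this window and no power for these outcomes. The only planning figure for loss, 30% over one year (Section 13.3), belongs to MVSS at 12 months. All rates below are assumptions.

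**Expected rate in one arm.** Let dL be the share lost after eschar removal (excepted), dW the share of other discontinuers (blanked), p, pL and pW the true readmission risks in completers, lost and other discontinuers, and f the share of events seen before leaving.

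- SAP rate = [(1 − dL − dW)·p + dL·pL·f] / (1 − dW)
- True rate = (1 − dL − dW)·p + dL·pL + dW·pW

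Assume p = 15% and f = 0.5.

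1. Leavers at twice the risk (pL = pW = 30%):
   - dL = dW = 2%: SAP (0.144 + 0.003)/0.98 = 15.0%; true 0.144 + 0.006 + 0.006 = 15.6%. Difference −0.6 points.
   - dL = 10%, dW = 5%: SAP (0.1275 + 0.015)/0.95 = 15.0%; true 0.1275 + 0.03 + 0.015 = 17.25%. Difference −2.25 points.
   - dL = 20%, dW = 10%: SAP (0.105 + 0.03)/0.90 = 15.0%; true 0.105 + 0.06 + 0.03 = 19.5%. Difference −4.5 points.
   - The SAP rate stays at 15.0% only because pL·f happens to equal p here.
2. Equal risk of 15% in everyone:
   - dL = 10%, dW = 5%: SAP (0.1275 + 0.0075)/0.95 = 14.2%; true 15.0%. Difference −0.8 points, all from the lost-to-follow-up assumption.
   - dL = 0, dW = 10%: SAP 0.135/0.90 = 15.0%; true 15.0%. The deletion is neutral.
3. Deletion alone (dL = 0, dW = 10%), so SAP 0.135/0.90 = 15.0%:
   - pW = 30%: true 0.135 + 0.03 = 16.5%. Difference −1.5 points.
   - pW = 0: true 13.5%. Difference +1.5 points.

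**Count example.** With 145 patients (Section 13.3) allocated 1:1 (Section 11.1.11), an arm has about 72. Suppose 62 complete with 10 readmitted, 5 are lost after eschar removal with 1 readmission recorded, and 5 discontinue otherwise.

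- The SAP reports (10 + 1)/(62 + 5) = 11/67 = 16.4%, whether those last 5 had no recorded readmission or all 5 had one.
- Recorded events over all patients run from 11/72 = 15.3% to 16/72 = 22.2%.
- If 0 to 4 of the lost patients had an unseen later event, the rate on the SAP denominator runs from 11/67 = 16.4% to 15/67 = 22.4%.

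**Side by side in the SAP.** Section 10.2 refers missing values to Section 10.1, which has no rule for readmission or transfusion. Antibiotic days, also in Section 10.3.4.4, are blanked with no lost-to-follow-up exception. Missing-data sensitivity analyses are planned for eschar removal, surgical excision and autograft incidence (Sections 10.1.2, 10.1.3.1, 10.1.3.4), but not here.

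**The case against.** The rule is pre-specified, its reasoning is given, and it applies equally to both arms. Readmission and transfusion are additional safety endpoints (Section 7.2.3.6) outside the testing hierarchy (Section 11.1.9). Section 10.5.2 says almost all patients were past the 12-week visit when COVID-19 broke out. That is not a dropout rate, but it gives no support for assuming heavy pandemic-related loss in this window. All of this stands and limits the weight of the point.

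Four stronger readings are tempting, and the documents do not support them:

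- **That the rates are understated.** Only the lost-to-follow-up assumption has a fixed direction. Blanking removes a patient from numerator and denominator, so its effect depends on that patient's risk.
- **That every lost patient is assumed event-free.** The exception covers only those who completed eschar removal; other lost patients are blanked.
- **That MW2010 shows unseen events after loss.** The remark concerns observed readmissions and explains why the data of lost patients are kept. It shows that loss and readmission were related there, not that later events were missed.
- **That safety events disappear from the report.** Events reported as AEs or SAEs remain in the tables of Section 11.1.5.4, and Section 10.3.4.4 lists all SAEs for the enrolled population. Transfusions during eschar removal also enter the blood-loss endpoint, where no such deletion is stated. The rule affects the readmission and transfusion summaries and their tests.

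**Conclusion.** The point holds in a limited form. For discontinuers outside the exception, the SAP removes readmission values already fixed at yes and transfusion volumes already complete for a period. For the excepted lost patients it assumes no later event. No planned analysis would show the effect of either choice. Deaths are covered only if they count as discontinuation, which the rule does not say.

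The size is not computable from the documents. The illustrated range, 4.5 points down to 1.5 points up in one arm's readmission rate, rests wholly on the assumed risks, dropout shares and f = 0.5. A between-arm bias further requires that discontinuation, or its link with the event, differ by arm; the documents neither show nor exclude this. The primary and secondary efficacy conclusions are not affected.

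**What to change.** In the safety set:

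1. **Readmission.** Analyse time from initial discharge to first readmission (overall, planned, unplanned), censored at last contact, with death as a competing event. State that censoring is assumed non-informative; the method does not avoid an assumption about patients after loss. Add simple bounds for lost patients, such as none or all of those without a recorded readmission having one later.
2. **Transfusion.** Keep the observed volume for every period a patient completed (before treatment, eschar removal, within one week, later). Show discontinuers separately for the period they did not complete.
3. **Present rule.** Retain it as a sensitivity analysis.

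Merely restoring recorded yes values while leaving the other discontinuers missing would not do. With equal risks of 15%, f = 0.5, dL = 0 and dW = 10%, it gives (0.135 + 0.0075)/(0.90 + 0.0075) = 15.7% against a true 15.0%.

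The cost is some SAP wording and one extra table, assuming that readmission dates are in the eCRF; Section 10.3.4.4 names the reason for readmission but not its date. The SAP already uses censoring and a log-rank test for duration of hospitalization (Sections 10.3.5.8 and 11.1.6.9), so survival methods are not new to the plan.
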